16.2. SECONDARY EFFICACY

The key secondary efficacy endpoint is:

 The incidence of participants who have a post-treatment response (negative at baseline to positive at any time post-baseline) for SARS-CoV-2 nucleocapsid antibodies

The other secondary efficacy endpoints are:

- The incidence of SARS-CoV-2 RT-PCR-positive severe or critical symptomatic illness occurring post dose of IMP
- The incidence of COVID-19-related Emergency Department visits occurring after dosing with IMP

Please refer to Section 17 for other secondary endpoints related to PK and ADA data.

16.2.1. KEY SECONDARY EFFICACY ENDPOINT

The key secondary endpoint is the incidence of participants who have a post-treatment response (negative at baseline to positive at any time post-baseline) for SARS-CoV-2 nucleocapsid antibodies.

The primary and the key secondary efficacy hypotheses will be assessed by a hierarchical order. More details on multiplicity are provided in Section 7.4.

16.2.2. ESTIMANDS FOR KEY SECONDARY EFFICACY

The treatment condition of interest is single dose of AZD7442 (two IM injections, one for each mAb component, AZD8895 and AZD1061). The alternative treatment condition to which comparison will be made is a placebo.

The population of participants targeted in the key secondary estimand includes adults at 18 years of age who have not had a prior SARS-CoV-2 RT-PCR-positive confirmed COVID-19 infection and who are candidates for benefit

from passive immunization with antibodies, defined as having increased risk for inadequate response to active immunization (predicted poor responders to vaccines OR intolerant of vaccine), OR having increased risk for SARS-CoV-2 infection, defined as those whose locations or circumstances put them at appreciable risk of exposure to SARS-CoV-2 and COVID-19.

The key secondary endpoint (variable) to be obtained is a binary response, whereby a participant is defined as post-baseline positive if the participant has a positive serology test result for SARS-CoV-2 nucleocapsid antibodies from the validated assay performed at the central laboratory.

The estimand for the key secondary efficacy endpoint uses a while on treatment strategy. Data for participants who become unblinded to treatment assignment and/or take COVID-19 vaccine or other COVID-19 preventive product, in both cases prior to having met the criteria for the key secondary efficacy endpoint, are censored at the date of unblinding/receipt of first dose of COVID-19 preventive product, whichever is earlier.

The population-level summary measure is prophylactic efficacy, calculated as 1 – relative risk. (Relative risk is the incidence of infection in the AZD7442 group relative to the incidence of infection in the control group.)

16.2.3. OTHER SECONDARY EFFICACY ENDPOINTS

The following endpoints will be presented along with 95% CIs and p-values. These will be nominal, as they are not controlled for multiplicity.

16.2.3.1. The Incidence of SARS-CoV-2 RT-PCR-Positive Severe or Critical Symptomatic Illness Occurring Post Dose

The severity of COVID-19 will be evaluated in participants who test positive for SARS-CoV-2 by RT-PCR. A diagnosis of severe or critical COVID-19 will include laboratory-confirmed COVID-19 (SARS-CoV-2 RT-PCR-positive symptomatic illness) plus meeting the severity criteria. The calculation of the follow up time (included as offset in model) will be calculated by using date symptoms become severe as the reference date.

Severe COVID-19 is characterized by a minimum of either pneumonia (fever, cough, tachypnea, OR dyspnea, AND lung infiltrates) or hypoxemia (SpO2 < 90% in room air and/or severe respiratory distress) and a WHO Clinical Progression Scale score of 5 or higher. Data from the eCRF will be used to determine if the participant met the qualifying severe symptoms.

All COVID-19 severity data will be listed.

16.2.3.2. The Incidence of COVID-19-Related Emergency Department Visits Occurring After Dosing with IMP

Incidence of COVID-19-related Emergency Department visits is collected on the Emergency Room visit eCRF form. If there is any record with hospitalization status as ER with primary reason for ER visit selected as 'COVID-19 related symptoms', it is considered that the participant has an incidence of COVID-19-related emergency

department visit. The calculation of the follow-up time (included as offset in model) will be calculated by using the earliest start date of ER visit.

All Emergency Department visit data will be listed, regardless of primary reason for ER visit.

16.2.4. MISSING DATA IMPUTATION METHOD FOR SECONDARY EFFICACY ENDPOINTS

No imputation method will be used for the main analysis of the key secondary efficacy endpoint or for any analysis of other secondary efficacy endpoints.

16.2.5. ANALYSIS OF SECONDARY EFFICACY ENDPOINTS

The key secondary efficacy endpoint will be analyzed as described in Section 16.2.1.

All other secondary efficacy endpoints described in Section 16.2.3 above will be analyzed in the same manner as the primary analysis of the primary efficacy endpoint (refer to Section 16.1.4), prior to Day 183. These analyses will be repeated for these endpoints through Day 183 and through Day 366.

The key secondary efficacy endpoint will be assessed by a hierarchical order. More details on multiplicity control are described in Section 7.4. For the other secondary efficacy endpoints, the 95% CIs and p-values will be nominal as they are not controlled for multiplicity.

16.2.6. SENSITIVITY ANALYSES FOR SECONDARY EFFICACY ENDPOINTS

No sensitivity analysis will be performed for any secondary efficacy endpoints.

16.2.7. SUPPLEMENTARY ANALYSES FOR SECONDARY EFFICACY ENDPOINTS

For all secondary efficacy endpoints (Section 16.2.3), the incidence of each endpoint will be presented graphically using Kaplan-Meier curves with log-rank test p-value.

16.2.8. SUBGROUP ANALYSES FOR SECONDARY EFFICACY ENDPOINTS

Subgroup analyses for secondary endpoints will be conducted if their sample is sufficient. The same methodology for the primary endpoint will be employed (refer to Section 16.1.7). If the model will not converge because the sample is too small, then only descriptive statistics such as counts and percentages and where applicable continuous summary statistics will be presented.

16.3. EXPLORATORY EFFICACY

The exploratory efficacy endpoints are:

- The incidence of the first case of SARS CoV-2 RT-PCR-positive symptomatic illness occurring after dosing with IMP through Day 366
- Viral genome copies in NP swabs collected at Illness Visits as determined by qRT-PCR (Illness Visits only)
- Duration of SARS-CoV-2 shedding in saliva over time (Illness Visits only)
- Genotypic analysis and biochemical and/or susceptibility analysis of SARS-CoV-2 variants to AZD7442 (Illness Visits only)
- Biophysical parameters, including, but not limited to serial measurements of skin temperature, heart rate, respiratory rate, blood oxygen saturation, and physical activity, recorded using a biosensor from Illness Visits Day 1 through Day 28
- Symptoms recorded by participants in an Illness e-Diary from Illness Visits Day 2 through Day 28.

Only nominal p-values will be provided for exploratory efficacy endpoints (see Section 7.4). Please refer to Section 17 for exploratory endpoints related to PK and PD data.

16.3.1. EXPLORATORY EFFICACY ENDPOINTS

16.3.1.1. The Incidence of the First Case of SARS-CoV-2 RT-PCR-Positive Symptomatic Illness Occurring after Dosing with IMP through Day 366

An exploratory endpoint is the incidence of the first case of SARS-CoV-2 RT-PCR-positive symptomatic illness occurring after dosing with IMP through Day 366. The criteria for determining this endpoint is the same as those for the primary efficacy endpoint (see Section 16.1.1) except that the endpoint will only be evaluated within the specified efficacy evaluation period, through Day 366. The analysis will be performed on the full pre-exposure analysis set. This endpoint will be analyzed as described in Section 16.2.1.

To assess the durability of efficacy analyses for the incidence of the first case of SARS-CoV-2 RT-PCR-positive symptomatic illness occurring after dosing with IMP through Day 366, single-arm descriptive summaries over the Day 366 follow-up period for participants who received AZD7442 with no censoring for unblinding intercurrent events will be presented. However, if a participant receives a COVID-19 vaccine or COVID-19 preventive product, their follow-up will be censored at the date of first administration of that product.

16.3.1.2. Viral Genome Copies in NP Swabs Collected at Illness Visits as Determined by qRT-PCR

An exploratory efficacy endpoint is the viral genome copies in NP swabs which will be collected via SARS-CoV-2 RT-PCR test at central laboratory at Illness Visits as described in protocol section 1.3. The analysis will be performed on the full pre-exposure analysis set. Observed and change from baseline for Illness Visits (as defined in Section 6.5) in viral load will be summarized by planned treatment group and time points for the Illness Visits. A

logistic regression analysis of the proportion of participants with viral load $>10^4$ copies/mL may be performed. In addition, the number of weeks of high viral load ($>10^4$ copies/mL) among participants may be performed using a Stratified Wilcoxon rank sum test.

A listing will be provided for all viral genome copy data, regardless of RT-PCR result. Indicators will be included in listings of illness visits to distinguish those with positive RT-PCR results from those with negative RT-PCR results.

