7.1. SAMPLE SIZE CALCULATION

Approximately 5150 participants will be randomized in a 2:1 ratio to receive a single IM dose of AZD7442 (divided in 2 sequential injections, one for each mAb component) (the active group, n = approximately 3433) or saline placebo (the control group, n = approximately 1717) on Day 1.

The sample size calculations are based on the primary efficacy endpoint and were derived following a modified Poisson regression approach (Zou 2004). All participants will be followed for the entire duration of the study.

With at least 18 observed events, assuming 80% true efficacy, the study will have approximately 90% power to demonstrate that the lower bound of the 2-sided 95% CI for efficacy is greater than 0 (see Table L:).

Table L: Simulated Power by Number of Observed Events

$\lambda_{Placebo}$	$\lambda_{AZD7442}$	Observed Events	Simulated Power
0.0074	0.0015	18	89%
0.0082	0.0016	20	96%
0.0090	0.0018	22	97%
0.0098	0.0020	24	98%

Simulated power is based upon 10000 simulations of trials assuming 80% efficacy $\left(1 - \frac{\lambda_{AZD7442}}{\lambda_{Placebo}}\right)$, using Poisson regression model with robust variance, with no participants lost follow-up. Power is the proportion of trials with p-value < 0.05.

The sample size necessary to achieve the power for the primary endpoint is calculated based on the assumed attack rate in the placebo group and the 80% efficacy assumption, using Poisson regression model with robust variance.

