7.3. STATISTICAL TESTS

Statistical tests will be conducted at the two-sided 5% significance level. Confidence Intervals (CIs) will be two-sided with 95% coverage.

The null hypothesis for the primary endpoint is: efficacy of AZD7442 compared to placebo in preventing COVID-19 is equal to 0. Whereas, the alternative hypothesis is: efficacy of AZD7442 compared to placebo in preventing COVID-19 is not equal to 0. That is:

H0: efficacy = 0

HA: efficacy $\neq 0$

Primary efficacy will be presented with a 2-sided 95% CI, and statistical significance will be achieved if the lower bound of the 2-sided 95% CI is > 0. The success criterion for the study will be statistical significance.

If the statistical significance of the primary efficacy endpoint is demonstrated at two-sided alpha of 0.05, formal assessments of the key supportive estimands and key secondary estimand will be conducted at the primary analysis.

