 - o If an end of study date occurs prior to Day 183, the efficacy follow-up time will be calculated as (Date of End of Study or Date of Last Assessment, whichever is later) (Date of Dosing) + 1.
 - o If an end of study date occurs after Day 183, the efficacy follow-up will be censored at Day 183.

For participants who continue to participate in the study at the time of the primary analysis, the DCO date will be used as their last assessment date. For participants with no post-baseline visit data available, the date of IMP administration will be used i.e. follow-up will be 1 day.

Efficacy is the incidence of infection in the AZD7442 group relative to the incidence of infection in the placebo group, expressed as a percentage. Efficacy will be calculated as relative risk reduction (RRR) = 100% x (1 - relative risk).

RRR and its corresponding 2-sided 95% CI will be estimated from the Poisson regression model with robust variance. In addition, the 2-sided p-value testing null hypothesis that there is no difference in efficacy between AZD7442 and placebo (i.e. the efficacy is equal to 0) will be obtained from the model. Statistical significance will be achieved if the lower bound of the 95% CI for efficacy is > 0, which corresponds to an observed two-sided p-value < 0.05. For the final analysis nominal 95% CI's will be presented.

The Poisson regression with robust variance analysis will be implemented by using the SAS PROC GENMOD procedure with the REPEATED statement for participant ID and logarithm link as well as OFFSET option. The estimated parameter $\hat{\beta}$ [i.e., log(RR)], 2-sided 95% confidence interval (CI) for $\hat{\beta}$, and the 2-sided p-value will be obtained from the SAS outputs. The estimated RR and corresponding CI for the RR is given by exponentiating $\hat{\beta}$ and its confidence limits. Therefore, the percent of RRR is given by $[(1 - \exp(\hat{\beta})) * 100\%]$. The CI for the percent of RRR is given by ([1 - exp(upper confidence limit for $\hat{\beta}$) * 100%], [1 - exp(lower confidence limit for $\hat{\beta}$) * 100%]).

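### For symptomatic COVID-19, SAP 16.3.1.1 judges durability of efficacy from AZD7442-arm incidence alone, and the cumulative randomised Day 366 estimate dilutes any late loss of efficacy

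*SAP*

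**What the plan says.** SAP 16.1.4 defines the quantity at issue as a comparison between arms: "Efficacy is the incidence of infection in the AZD7442 group relative to the incidence of infection in the placebo" group, expressed as a percentage.

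SAP 16.3.1.1 covers first symptomatic RT-PCR-positive illness from dosing through Day 366 and plans two things.

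- **A randomised analysis.** Table D gives its estimand: one value of 1 − relative risk, with follow-up censored at unblinding or at the first COVID-19 preventive product. For the method the SAP says "This endpoint will be analyzed as described in Section 16.2.1". Section 16.2.1 defines the key secondary endpoint and points to the multiplicity section; it contains no model.
- **A durability summary.** For this purpose "single-arm descriptive summaries over the Day 366 follow-up period for participants who received AZD7442 with no censoring for unblinding intercurrent events will be presented". Follow-up is censored at a COVID-19 vaccine or preventive product. No placebo, external or calendar-time comparator is named.

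Other sections limit what else is available:

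- Sections 16.3.3 and 16.3.4 plan no sensitivity or supportive analysis for exploratory endpoints.
- The Kaplan-Meier and Cox analyses in 16.1.6 belong to the primary endpoint, which ends before Day 183.
- Section 16.2.5 repeats the severe-illness and emergency department analyses through Day 366, and 16.2.7 adds Kaplan-Meier curves for them.
- On inferential status, section 16.3 says "Only nominal p-values will be provided for exploratory efficacy endpoints".

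**The concern.** The summary that carries the durability label has no comparator, so by the SAP's own definition it does not measure efficacy. If the attack rate falls after Day 183, AZD7442 incidence can stay low with no protection left. If the attack rate rises, incidence can climb with protection intact. A steady attack rate cannot be presumed: the protocol addendum's amendment summary speaks of new variants rising in prevalence.

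The randomised estimate through Day 366 does have a comparator, but it averages the whole period from dosing. If unblinding and vaccination remove much of the later follow-up, the early months dominate the average. What is at stake is how the final report describes the length of protection from one dose. The primary result is not at stake.

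**Working it through.** **Inputs from SAP 7.1.** "Approximately 5150 participants will be randomized in a 2:1 ratio": 3433 to AZD7442 and 1717 to placebo. The 24-event row of Table L has placebo risk 0.0098 and AZD7442 risk 0.0020, which is about 80% efficacy.

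**Assumptions, not in the documents.** Table L gives no time span; I read 0.0098 as the risk from dosing to Day 183. The late background multiplier (m), the share of late follow-up still uncensored (f, equal in both arms unless stated) and late efficacy are shown as ranges.

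**The plan's own figure.** Table L gives simulated power of 89%, 96%, 97% and 98% at 18, 20, 22 and 24 events. Fixing the event total, splitting it binomially between arms and applying a two-sided 5% Wald test to the log risk ratio gives 88.0%, 96.8%, 97.2% and 97.6%. Table L reproduces and is not in dispute. The SAP states no design figure for Day 366 or for durability.

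**Step 1: the single-arm summary.** Late AZD7442 risk = 0.0098 × m × (1 − late efficacy). Early risk = 0.0098 × 0.2 = 1.96 per 1000, or 3433 × 0.00196 = 6.7 cases.

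| Late AZD7442 risk per 1000 (cases in 3433) | Combinations that give it |
|---|---|
| 1.96 (6.7) | 80% efficacy, m = 1; 60%, m = 0.5; 0%, m = 0.2 |
| 5.88 (20.2) | 40% efficacy, m = 1; 80%, m = 3 |
| 9.80 (33.6) | 0% efficacy, m = 1; 80%, m = 5 |

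An unchanged rate fits late efficacy anywhere from 0% to 80%.

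Taking early and late case counts as independent Poisson variables with full follow-up:

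- If efficacy is 0% after Day 183, late cases do not exceed early cases with probability 24%, 55% or 89% at m = 0.3, 0.2 or 0.1.
- If efficacy stays at 80%, late cases exceed early cases with probability 92% at m = 2 and more than 99.9% at m = 5.

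**Step 2: the cumulative randomised estimate.** With early efficacy 80%, cumulative efficacy = 1 − [0.2 + f·m·(1 − late efficacy)] / (1 + f·m). With m = 1 and late efficacy 0%:

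- f = 0.10: 1 − 0.30/1.10 = 73%
- f = 0.25: 1 − 0.45/1.25 = 64%
- f = 0.50: 1 − 0.70/1.50 = 53%
- f = 1: 1 − 1.20/2.00 = 40%

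Unequal censoring also moves the figure. If late follow-up is 0.2 of early follow-up on placebo and 0.6 on AZD7442, and true efficacy stays at 80%, the cumulative rate ratio gives 74% at m = 3: 1 − [(0.2 + 0.36)/1.6] / [(1 + 0.6)/1.2]. At m = 0.5 it gives 82%.

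**Step 3: what a period split could deliver.** Late events at m = 1 are 1717 × 0.0098 × f = 16.83f on placebo and 33.64f × (1 − late efficacy) on AZD7442. SE of the log rate ratio = √(1/placebo events + 1/AZD7442 events), and the 95% limits are 1 − RR × exp(±1.96 SE).

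| f | Late events at true 80% (placebo, AZD7442) | 95% CI, true 80% | 95% CI, true 0% |
|---|---|---|---|
| 0.50 | 8.4, 3.4 | 29% to 94% | −129% to 56% |
| 0.25 | 4.2, 1.7 | −20% to 97% | −222% to 69% |
| 0.10 | 1.7, 0.7 | −238% to 99% | −536% to 84% |

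These are large-sample intervals and are rough at such counts.

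**The case against.** The case on the other side is substantial, and most of it stands as a limit on scope.

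- **A reader might infer that no other randomised comparison reaches Day 366.** That is not so. Sections 16.2.5 and 16.2.7 carry severe illness and emergency department visits to Day 366 with the 16.1.4 model and Kaplan-Meier curves. The gap is for all symptomatic illness, and for a period split of any of these endpoints.
- **A reader might infer that the cumulative estimate conceals late loss altogether.** It does not: in Step 2 it falls from 80% to between 73% and 40%. If events and person-time by arm were shown both before Day 183 and through Day 366, late efficacy would follow by subtraction. The SAP does not promise that layout.
- **A reader might infer that the repeat-dose intervals rest on this summary.** Protocol 4.2 bases them on the antibody's half-life and expected clinical need, and evaluates them through serum concentrations. Nothing makes them depend on 16.3.1.1.
- **The single-arm summary is an addition to the randomised analysis.** It is openly single-arm and descriptive, and uses AZD7442 follow-up that Table D discards at unblinding. That justifies keeping it. It does not justify calling it durability of efficacy.
- **The period split is weakest where dilution is worst.** At 10% or 25% uncensored, the intervals for true 80% and true 0% overlap heavily, so it could not separate lasting from lost protection. SAP 4.4 itself expects unblinding to reduce observable events. A wide interval still shows that uncertainty, and a single-arm rate does not.

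**Conclusion.** The concern holds for all symptomatic COVID-19. The AZD7442-only summary in 16.3.1.1 cannot identify efficacy over time. The Table D estimate through Day 366 is cumulative and dilutes late loss: complete loss after Day 183 still reads 73%, 64% or 53% with 10%, 25% or 50% of late follow-up uncensored. Those figures assume flat background, 80% early efficacy and equal censoring by arm; the documents give no late retention or background rate. That the estimate is cumulative rests on the endpoint and on Table D, since the cited method section has no model. If 16.1.4 is meant, its terms are treatment and age group with a follow-up offset, and nothing for period.

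The endpoint is exploratory and outside the testing hierarchy in 7.4, so no confirmatory conclusion changes. The fault lies in the label and in a missing period-specific comparison.

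**What to change.** In SAP 16.3.1.1:

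1. Add a randomised period-specific analysis: the 16.1.4 Poisson model with follow-up split at Day 183, a treatment-by-period term and Table D censoring. The participant-level REPEATED statement in 16.1.4 already accommodates two records per person.
2. For dosing to Day 182 and for Day 183 to 366, report events, person-time and number at risk per arm, and efficacy with its 95% CI.
3. State that the late-period estimate is descriptive and may be uninformative if little uncensored placebo follow-up remains. Note that it compares only participants still event-free and uncensored at Day 183, so unequal censoring by arm could bias it.
4. Keep the single-arm summary, labelled AZD7442-arm incidence and not durability of efficacy.

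Separately, as an editorial correction, change the method reference from 16.2.1 to 16.1.4. Section 16.2.5 sends the key secondary endpoint to the same place, so correct it there too.

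The cost is SAP wording, one further model and one table on data already collected. The price in interpretation is a late interval that may be too wide to settle the question.

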16.3.1.3. Duration of SARS-CoV-2 Shedding in Saliva Over Time (Illness Visits only)

Viral Shedding

An exploratory efficacy endpoint is the duration of SARS-CoV-2 shedding in saliva over time. The analysis will be performed on the full pre-exposure analysis set. Saliva samples for viral shedding will be collected at Illness Visits as described in protocol section 1.3. The number and proportion of participants shedding on Illness Visits planned in the protocol Schedule of Assessments will be summarized. Exact 95% CIs using Clopper-Pearson method for binomial proportions will be computed.

The duration of SARS-CoV-2 shedding in saliva will be calculated as following:

Duration (days) = (Date of Illness Visit when viral shedding first tested as persistently negative or date of last Illness Visit when test was positive, if no negative test is available) – Date of first positive + 1.

The number of days of shedding will be summarized by descriptive statistics.

A listing will be provided for all viral shedding data, regardless of RT-PCR result. Indicators will be included in listings of illness visits to distinguish those with positive RT-PCR results from those with negative RT-PCR results.

• Viral Quantitation

For values reported as lower than the lower limit of quantification (LLOQ), a value equal to half of the limit of quantification will be imputed in viral quantitation summaries. Missing values will not be imputed in viral quantitation summaries.

For the subset of participants who shed, viral quantities as measured by qRT-PCR will be summarized for Illness Visits planned in the protocol Schedule of Assessments. Summary statistics will be presented describing the mean, standard deviation, median, minimum and maximum of Log10 (viral copies/mL) at Illness Visit baseline (Date of first positive) and each post-baseline time-points.

Change and percent change from Illness Visit baseline at each post-baseline time point will also be summarized.

Time weighted change from Illness Visit baseline to each post-baseline time-point is derived on a by-participant basis using the linear trapezoidal rule with all available data from baseline to that specific time-point minus the baseline value. This is defined as (Area Under the Curve [AUC])/number of days – Illness Visit baseline value, between Illness Visit baseline to that specific post-baseline time-point. AUC from Illness Visit baseline to each post-baseline time-point will be reported as well.

Figures such as Log_{10} (viral copies/mL) over time (mean \pm SD), AUC and time weighted change from Illness Visit baseline of Log_{10} (viral copies/mL) over time (box plots) will be provided.

16.3.1.4. Genotypic Analysis and Biochemical and/or Susceptibility Analysis of SARS-CoV-2 Variants to AZD7442 (Illness Visits Only)

An exploratory efficacy endpoint is the Genotypic analysis and biochemical and/or susceptibility analysis of SARS-CoV-2 from NP swabs collected at Illness Visit baseline. This analysis will not be covered in this SAP.

16.3.1.5. Biophysical Parameters, Including But Not Limited to Serial Measurements of Skin Temperature, Heart Rate, Respiratory Rate, Blood Oxygen Saturation, and Physical Activity, Recorded Using a Biosensor From Illness Visits Day 1 Through Day 28

A group of efficacy endpoints are biophysical parameters collected from Current Health wearable device. The analysis of these exploratory endpoints results is not covered in this SAP.

16.3.1.6. Symptoms recorded by participants in an Illness e-Diary from Illness Visits Day 2 through Day 28

A group of exploratory endpoints are symptoms collected by participants in an illness e-Diary. Symptoms from the first SARS-CoV-2 RT-PCR-positive symptomatic illness occurring post dose will be summarized. The number and percentage of participants with these symptoms, onset study day of these symptoms, and the duration days will be summarized by treatment group. The analysis will be based on participants in the full pre-exposure analysis set.

All symptoms from each illness visit will be listed, regardless of RT-PCR result. Indicators will be included in listings of illness visits to distinguish those with positive RT-PCR results from those with negative RT-PCR results.

